5.4.2. MASKING PROCEDURES

The PI, Co-Investigator, and any members of the research staff who will be analyzing study data will be masked to participant treatment. The Research Coordinator and any study staff who will be involved in the treatment of the study participants on the HD-tDCS study days will be unmasked.

5.5. REASONS FOR WITHDRAWAL

Subjects are free to withdraw from participation in the study at any time upon request.

An investigator may terminate a study subject's participation in the study if:

- Any clinical adverse event (AE), laboratory abnormality, or other medical condition or situation occurs such that continued participation in the study would not be in the best interest of the subject.
- The subject meets an exclusion criterion (either newly developed or not previously recognized) that precludes further study participation.

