5.2. SUBJECT EXCLUSION CRITERIA

An individual who meets any of the following criteria will be excluded from participation in this study:

- Presence of any other systemic or chronic pain disorder
- History or current evidence of a psychotic disorder (e.g. schizophrenia) or substance abuse; bipolar or severe major depression, as evidenced by Beck Depression score of ≥ 20*
- Prior use of tDCS
- Ongoing, unresolved disability litigation
- History of neurological disorder (e.g. epilepsy, stroke, neuropathy, neuropathic pain)
- Current use of opioid pain medications
- Allergic response to study radiotracers or chemically-related drugs
- Excluded by MRI Center or PET Center safety screening checklist (as administered by study staff)
- Female participants who are pregnant, nursing, or planning a pregnancy, or who are of childbearing potential and are not using a reliable means of contraception during the baseline and study periods (negative urine pregnancy test must be available before any procedures are initiated)
- Treatment with an investigational drug, device or other intervention within 30 days of study enrollment (Screening Visit).
- Anything that would place the individual at increased risk or preclude the individual's full compliance with or completion of the study (eg, medical condition, laboratory finding, physical exam finding, logistical complication).

^{*} The Beck Depression Inventory will be graded by study staff at the time of completion. Individuals with a score of ≥ 30 will be provided with a pamphlet from the Michigan Depression Center that contains information and contacts regarding depression. In addition, those individuals who respond to question #9 with answers #2 or #3, will be provided with a flyer from the Department of Health and Human Services National Suicide Prevention Lifeline (800 number and website).

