5.6. HANDLING OF WITHDRAWALS

Subjects wishing to withdraw from the study at any time may notify the study team.

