7.5. FINAL STUDY VISIT

Follow Up Month 2 (Day 65 ± 2)

The final visit will consist of adverse event collection, review of concomitant medications, the completion of questionnaires, and – if applicable – instructions regarding the follow-up of ongoing adverse events.

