7.6. EARLY TERMINATION VISIT

If a subject terminates the study early for one of the reasons listed in Section 5.5 or 5.6, and is willing to return to the site for a final study visit, the following will be completed:

- · Record adverse events as reported by subject or observed by investigator
- Provide final instructions to subject (e.g., follow-up of ongoing adverse events)

If the subject can not be reached or is not willing to return to the study site for a final study visit, the subject will be considered lost to follow up.

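### Section 5.5 can end a randomised patient's whole participation on a newly developed exclusion criterion, and nothing keeps the remaining pain questionnaires for Aim 2

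*Combined protocol and SAP*

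**What the plan says.** Section 5.5 opens with "An investigator may terminate a study subject's participation in the study if" and lists two grounds. One is a medical condition or situation in which continuing is not in the subject's best interest. The other reads "The subject meets an exclusion criterion (either newly developed or not previously recognized) that precludes further study participation". The exclusion criteria in Section 5.2 include "Current use of opioid pain medications" and "Female participants who are pregnant, nursing, or planning a pregnancy".

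Section 5.6, on handling withdrawals, consists of one sentence: "Subjects wishing to withdraw from the study at any time may notify the study team". It does not mention continued data collection.

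Section 7.6 covers the exit visit. It applies "If a subject terminates the study early for one of the reasons listed in Section 5.5 or 5.6", provided the subject is willing to return, and has two items: "Record adverse events as reported by subject or observed by investigator", and final instructions. In the Appendix A schedule, the early termination column is marked for adverse events and for no pain questionnaire.

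The planned follow-up is light. Section 7.4 describes the follow-up visits as adverse events, concomitant medications and questionnaires. Section 7.5 says of Month 2: "The final visit will consist of adverse event collection, review of concomitant medications, the completion of questionnaires". Appendix A schedules the short-form McGill, GeoPain, the visual analogue pain scale and the allodynia questionnaire at Week 1, Month 1 and Month 2.

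**The concern.** Section 5.5 allows an entry criterion to be applied after randomisation, and the only exit it describes is from the whole study. Some criteria may be met as a consequence of the condition being treated. A patient who starts an opioid because attacks are worse might be judged to meet the opioid criterion and be removed, with no pain score at exit or later.

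Aim 2 compares active with sham on clinical pain measures. If the patients removed tend to be those in most pain, the remaining scores in that arm look better than they should. If this happens more in the sham arm, a real benefit is diluted. If it happens more in the active arm, benefit is overstated or worsening pain is partly concealed. The 20% dropout allowance in Section 11.2 replaces numbers. It does not correct for which patients are missing.

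**Working it through.** **What can be lost, and when**

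1. Randomisation takes place at Screening or PET/MRI #1, before Day 0 (Appendix A and its footnote on randomisation).
2. A new exclusion criterion can come to light afterwards. Appendix A repeats the pregnancy test and drug screen at PET #2 (Day 16 ± 2) and reviews concomitant medications at every visit from Screening to Month 2.
3. If participation is then ended under Section 5.5, Section 7.6 governs: adverse events and final instructions only. Section 5.6 adds nothing.
4. The remaining questionnaires, up to Month 2 (Day 65 ± 2), are therefore not provided for. None of those visits includes PET, MRI or HD-tDCS, so a reason to stop a procedure does not in itself prevent them.

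**The plan's own figure**

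Section 11.2 gives 24 evaluable per group and a possible 20% dropout: 24 / (1 − 0.20) = 30 per group. This reproduces the stated 30. The plan thus tolerates a loss of 30 − 24 = 6 per arm, with no cause specified.

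**Size of a possible bias (illustration)**

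Assumptions that are not in the documents: pain scores are normal, the patients removed from one arm are exactly those with the worst scores, and any loss in the other arm is unrelated to pain. Removing the worst fraction q moves the arm's mean towards improvement by

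shift = φ(z) / (1 − q), in SD units, where z is the (1 − q) quantile of the standard normal and φ is its density.

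| Removed of 30 | q | z | φ(z) | Shift (SD) |
|---|---|---|---|---|
| 1 | 0.033 | 1.834 | 0.0742 | 0.0742/0.9667 = 0.08 |
| 2 | 0.067 | 1.501 | 0.1293 | 0.1293/0.9333 = 0.14 |
| 3 | 0.100 | 1.282 | 0.1755 | 0.1755/0.9000 = 0.19 |
| 6 | 0.200 | 0.842 | 0.2800 | 0.2800/0.8000 = 0.35 |

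Under these assumptions the active-minus-sham contrast moves by the same amount.

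For scale, a two-sided 0.05 t-test with 24 per group has 80% power for a difference of about 0.83 SD. (Section 11.2 pairs 24 per group with an effect size of 1.2, which is a separate matter.) The extreme bound is 0.35/0.83 = 42% of that difference, and a single removal is 0.08/0.83, about 10%.

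**The case against.** **The rule is narrower than it may look.** Section 5.5 is discretionary and applies only to a criterion that precludes further participation. A reader might infer that any patient who takes an opioid or becomes pregnant must leave. The text does not say so. Because Month 1 and Month 2 involve no procedure, an investigator could judge that neither condition precludes them. Appendix A labels the pregnancy test and drug screen as a safety screen for the tracer, and Section 9.3.4 on pregnancy asks for notification and reporting, not termination. This stands: removal is permitted, not required. It does not answer the point, because no section says which criteria preclude which procedures or that questionnaires continue.

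**The opioid route is inferred.** Current use is not defined, entrants have taken no opiates for six months (Section 5.1), and no document links worsening headache to opioid use or gives a frequency. This stands. A reader might also cite pregnancy as evidence of outcome-related removal. It illustrates lost follow-up only, since it is not a sign of worsening pain.

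**0.35 SD could be read as the expected bias.** It is not. It would assign the entire dropout allowance in one arm to pain-driven removal of exactly the six worst patients.

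**Harm is not wholly hidden.** Adverse events are recorded at an early termination visit if the patient attends one. What is lost is pain data. Aim 2 also names no single Month 1 or Month 2 endpoint, and pain response is a secondary outcome.

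**Other documents may deal with this.** The Statistical Analysis Plan and Manual of Procedures are separate and were not available. They may hold a retention or missing-data rule, but Section 5.5 would still permit the removal.

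**Conclusion.** The point holds as a gap in data collection with a possible bias. The protocol permits a study-level exit after randomisation on a newly developed exclusion criterion, offers no procedure-only exit, and collects no pain measure on the way out. Patients removed this way can lose every remaining pain questionnaire through Month 2.

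Whether this biases Aim 2 depends on removal being related to pain and differing between arms, and the documents settle neither. If it does occur, one to three such removals in an arm of 30 correspond to roughly 0.08 to 0.19 SD, with 0.35 SD for six as the extreme bound. These figures assume normality and removal of exactly the worst patients. If those removed are only partly the worst, the shift is smaller.

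The documents do not support saying that patients with worsening headache will be removed, or that the trial's comparison is biased. The change is still worth making: the missing assessments are inexpensive, and the loss cannot be repaired at analysis without assumptions about the unseen scores.

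**What to change.** Leave the investigator's clinical discretion in Section 5.5 as it is, including the best-interest ground. Add a data-collection rule to Sections 5.5, 5.6 and 7.6, and mark it in Appendix A:

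- It covers any randomised patient, including one not yet stimulated, whose procedures are stopped or whose participation the investigator ends. If the patient agrees, the remaining scheduled pain questionnaires, adverse event collection and medication review continue through Month 2.
- Such patients are analysed in their randomised arm for Aim 2.
- The start date of any opioid is recorded, so that affected BP_ND scans can be handled separately from the pain outcomes.

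The Week 1 visit day must be reconciled before the rule can refer to it: Section 7.4 prints Day 37 ± 2, the same as Month 1, while Appendix A prints Day 16 ± 2.

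The cost is a rewording of three sections and a few extra questionnaire contacts. The small downside is that some pain scores will be recorded after a change in analgesic. The concomitant medication review already in the schedule should show where this happened.

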5.6. HANDLING OF WITHDRAWALS

Subjects wishing to withdraw from the study at any time may notify the study team.

5.7. TERMINATION OF STUDY

This study may be suspended or prematurely terminated if there is sufficient reasonable cause. Written notification, documenting the reason for study suspension or termination, will be provided by the suspending or terminating party to the Principal Investigator and NIH-NINDS. If the study is prematurely terminated or suspended, the principal investigator will promptly inform the IRB and will provide the reason(s) for the termination or suspension.

Circumstances that may warrant termination include, but are not limited to:

- Determination of unexpected, significant, or unacceptable risk to subjects.
- Insufficient adherence to protocol requirements.
- Data that are not sufficiently complete and/or evaluable.
- Determination of futility.

6. STUDY INTERVENTION

6.1. STUDY PROCEDURAL INTERVENTION(S) DESCRIPTION

We will conduct a single-center, sham-controlled, double-blinded study to prospectively investigate the neuromodulatory effects of M1 HD-tDCS in pain intensity and brain molecular neuroplasticity in a cohort of episodic migraine patients. The subjects will participate in 10 daily sessions (eg, Monday – Friday for two weeks), either active or sham M1 HD-tDCS.

6.2. ADMINISTRATION OF PROCEDURAL INTERVENTION

In the active HD-tDCS group, stimulation will be applied for 20 minutes. For sham-controlled tDCS sessions current will be applied only for 30 seconds at the beginning and 30 seconds at the end of each 20-minute session, as sensations arising from tDCS treatment occur mostly at the beginning and end of application. Nonetheless, groups will be composed of tDCS-naïve patients to avoid comparison between sham and active from ongoing and previous experiences.

These HD-tDCS sessions will be conducted by study staff trained in the technique by the PI. Sessions will occur at the University of Michigan Hospital Systems (UMHS); hence, a licensed physician will be available by pager at all times.

6.3. PROCEDURES FOR TRAINING OF CLINICIANS ON PROCEDURAL INTERVENTION

All study clinicians will be trained in HD-tDCS technique by the PI (or trained designee) according to the study Manual of Procedures (MOP).

6.4. ASSESSMENT OF CLINICIAN AND/OR SUBJECT COMPLIANCE WITH STUDY PROCEDURAL INTERVENTION

Study staff performing each procedural administration will be trained in a standardized manner so as to assure compliance with the protocol. Likewise, the participation of study staff in subject scheduling will assist in their compliance with study procedures and instructions.

7. STUDY SCHEDULE

See Appendix A for a Schedule of Events.

7.1. PHONE PRESCREENING (DAY -56 TO -22)

Phone prescreening will take place for up to 8 weeks prior to Screening, to allow for scheduling of the Screening visits

7.2. SCREENING (DAY -21 TO DAY -1)

Screening will ideally take place during the week prior to the initial PET and MRI scans. The three-week window allows for scheduling of the PET and MRI visits up to three weeks following the Screening visit.

7.3. INTERMEDIATE VISITS

PET #1 (Day -21 to Day -1)

The PET scan will ideally take place during the week prior to the initial HD-tDCS session. The 21 day window allows for scheduling of the PET and MRI visits within three weeks of each other.

MRI #1 (Day -21 to Day -1)

The MRI will ideally take place during the week prior to the initial HD-tDCS session. The 21 day window allows for scheduling of the PET and MRI visits within three weeks of each other.

HD-tDCS #1-10, Day 0-4 and 7-111

On DAY 0, HD-tDCS will begin. Subjects will have been randomized prior to Day 0, but after consent has been provided.

PET #2 (Day 16 ± 2)

PET Scan #2 will take place during the week following HD-tDCS. If it cannot be scheduled during this week, it may be completed during the following week.

MRI #2 (Day 16 ± 2)

MRI #2 will take place during the week following HD-tDCS. If it cannot be scheduled during this week, it may be completed during the following week.

¹ M-F; missed days can be doubled within (M-F) x 2 schedule and with study team approval

7.4. FOLLOW-UP VISITS

Follow-up visits will consist of adverse event collection, review of concomitant medications, and the completion of questionnaires. All follow-up visit dates are calculated relative to the HD-tDCS visits. The Week 1 visit may be combined with either the PET #2 or MRI #2 visit.

Follow Up Week 1 (Day 37 ± 2)

Follow Up Month 1 (Day 37 ± 2)

7.5. FINAL STUDY VISIT

Follow Up Month 2 (Day 65 ± 2)

The final visit will consist of adverse event collection, review of concomitant medications, the completion of questionnaires, and – if applicable – instructions regarding the follow-up of ongoing adverse events.

7.6. EARLY TERMINATION VISIT

If a subject terminates the study early for one of the reasons listed in Section 5.5 or 5.6, and is willing to return to the site for a final study visit, the following will be completed:

- · Record adverse events as reported by subject or observed by investigator
- Provide final instructions to subject (e.g., follow-up of ongoing adverse events)

If the subject can not be reached or is not willing to return to the study site for a final study visit, the subject will be considered lost to follow up.

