11.2. SAMPLE SIZE CONSIDERATIONS

Taking into consideration a possible 20% dropout during the study, our sample size of 30 patients per group is a conservative number. For comparing two groups in Aim1 and Aim2, a sample size of 24 in each group will have 80% power to detect an effect size of 1.2 using a two-group t-test with a 0.05 two-sided significance level. For Aim3, baseline vs placebo/active M1 HD-tDCS, a sample size of 24 will have 80% power to detect an effect size of 0.8 using a paired t-test with a 0.05 two-sided significance level, allowing a wide range (0.1 to 1.0) of observable correlations within pairs.

Using the previous study, we approximated the SD as 20%/4 = 5% (range/4), and this gives us a detectable percentage change of 5*0.8=4 or higher.

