APPENDIX A: SCHEDULE OF EVENTS

APPENDIX B: QUESTIONNAIRES

APPENDIX A: SCHEDULE OF EVENTS

Procedures	Phone PreScreening (Dav –56 to -22)	Screening (Day-21 to -1)	PET/MRI #1 (Day -21 to -1)	HD-tDCS #1-10 (Days 0-4 & Days 7-112)	PET/MRI #2 (Day 16 ± 2)	Follow Up Week #1 (Day 16 ± 2)	Follow Up Month #1 (Day 37 ± 2)	Follow Up Month #2 Day 65 ± 2)	Early Termination ³
Prescreening Script/Checklist	X								Ш
Informed Consent		X							
Adverse Events		X	X	Х	Х	X	Х	Х	X
Medical/Dental History and Physical		X							
Medication History/ Concomitant Medications		X	X	Х	Х	X	х	Х	
Pregnancy Test (Dipstick) and Drug Screen ⁴			PET Only		PET Only				
Quantitative Sensory Testing (QST)			Х		Х				
Eligibility Assessment ⁵		X							
RANDOMIZATION		X ⁶	X ₆						
PET			X		Х				
Sustained Thermal Pain Threshold Stress (STPTS) PET Challenge			X		х				
Blood Sampling ⁷ Single Draw, Genetics Serial Samples, Biomarkers			PET Only		PET Only				
MRI			Х		Х				\square
HD-tDCS (M-F for 2 weeks)				10X8					

² Missed days can be doubled within the (M-F) x 2 schedule and with study team approval

³ If subject completes an in-person visit

⁴ Safety screen for ¹¹C-carfentanil

⁵ Schedule subject visits and provide subject with instructions (PET & MRI)

⁶ Subjects will be randomized after they have met eligibility and have been consented. This will occur prior to Day 0 ⁷ If subject has consented to sample future use sub-study.

⁸ See Section 6 for active vs healthy volunteer treatment paradigm

Procedures	Phone PreScreening (Dav –56 to -22)	Screening (Day -21 to -1)	PET/MRI #1 (Day -21 to -1)	HD-tDCS #1-10 (Days 0-4 & Days 7-11 ²)	PET/MRI #2 (Day 16 ± 2)	Follow Up Week #1 (Day 16 ± 2)	Follow Up Month #1 (Day 37 ± 2)	Follow Up Month #2 Day 65 ± 2)	Early Termination ³
Questionnaires									
Demographics		X ₉							
MIDAS Questionnaire		X ₉							
Beck Depression Inventory		X ₈							
"Expectation of Effect"		X							
McGill Pain Questionnaire (Long Form)		X							
McGill PQ (Short Form)		X	X	X	Х	Х	X	Х	
PANAS ⁹		X ₉	X ₉	X	Х	Х	X	Х	
GeoPain (via iPad)8		X	X	X	Х	Х	Х	Х	
Visual Analog Pain Scale ⁸		Х	X	X	Х	Х	Х	Х	\Box
Allodynia Questionnaire		Х	Х		Х	Х	Х	Х	\square
PET Subject Information Sheet			X ₉		Х				┌┤
Pittsburgh Sleep Quality Index		X ⁹				Х	Х	Х	
tDCS AE Questionnaire				X	Х	Х	Х	Х	┌┤
H.O.P.E. Questionnaire						X	X	Х	

⁹ At Screening, Before and After MRI/PET Scans and tDCS Sessions, and at Follow Up Visits

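### The early-termination visit records adverse events but no pain score, so a patient who comes in to leave the study gives no exit pain measure

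*Combined protocol and SAP*

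**What the plan says.** Section 7.6 covers a patient who ends the study early and "is willing to return to the site for a final study visit, the following will be completed". Two items follow: "Record adverse events as reported by subject or observed by investigator" and "Provide final instructions to subject (e.g., follow-up of ongoing adverse events". The second is not a measurement, so adverse events are the only data taken.

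Appendix A agrees. The Adverse Events row has eight marks, the last under Early Termination, a column qualified by the footnote "If subject completes an in-person visit". The rows for the short McGill, GeoPain, the VAS and concomitant medications have seven marks each and end at Month 2. The timing footnote for repeated questionnaires reads "At Screening, Before and After MRI/PET Scans and tDCS Sessions, and at Follow Up Visits" and does not name early termination.

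The scheduled visits differ. Section 7.4 states: "Follow-up visits will consist of adverse event collection, review of concomitant medications, and the completion of questionnaires". Section 7.5 says of Month 2: "The final visit will consist of adverse event collection, review of concomitant medications, the completion of questionnaires".

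Section 5.6 says only that a withdrawing subject may tell the study team. It does not describe continued outcome collection for someone who stops sessions. Section 11.2 sizes the groups "Taking into consideration a possible 20% dropout during the study".

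**The concern.** The patient is already on site, the instruments are already in use, and a visit of the same kind held on schedule would include them. The protocol gives no reason for leaving them out when the final visit comes early.

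What is at stake is Aim 2, the active-versus-sham comparison of pain. Section 5.5 lets the investigator end participation after an adverse event, and the rate of such events could differ by arm. Section 11 names t-tests, ANOVA and ANCOVA but no analysis set and no missing-data method. Section 11.1 has an analysis paragraph for Aim 1 and for Aim 3 but none for Aim 2. Section 11.6 defers the final analysis to a separate Statistical Analysis Plan, which is not in the text available here, so its handling of missing data cannot be judged. Whatever method it names, it cannot supply a score that was never taken.

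**Working it through.** **Inputs.** From section 11.2: 24 evaluable per group, 20% dropout, 30 per group. From section 4: 30 active and 30 sham. Assumed, because the documents give no figure: leavers in one arm differ from that arm's completers by δ = 0.25 to 1.0 SD.

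**1. The plan's own figure.** 24 / (1 − 0.20) = 30 per group, which reproduces. The allowance is 0.20 × 30 = 6 per arm, or 12 of 60 patients.

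**2. What a leaver's record contains.**
- Leaves before Day 0: scores from Screening, and from PET/MRI #1 if attended.
- Leaves during the two treatment weeks: also the pain questionnaires completed before and after each session attended (section 8.1.4).
- Leaves after treatment: also PET/MRI #2 and any follow-up visit attended.

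In each case no pain score is dated later than the last scheduled visit attended, even if the patient comes in for early termination.

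**3. Possible bias in a contrast between completers.** With dropout fraction p, the mean of all patients randomised to an arm is (1 − p) × m + p × (m + δ) = m + pδ, where m is the completer mean. If only one arm is affected, the completer contrast is off by pδ:
- δ = 0.25: 0.20 × 0.25 = 0.05 SD
- δ = 0.5: 0.20 × 0.5 = 0.10 SD
- δ = 1.0: 0.20 × 1.0 = 0.20 SD

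If both arms are affected at the same dropout rate, the error is p × (δ in active − δ in sham). It is zero when the two differences are equal.

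**4. Scale.** Section 11.2 names an effect size of 1.2 for Aim 2. Against that, 0.05 / 1.2 = 4% and 0.20 / 1.2 = 17%. By an exact two-sided t-test, 24 per arm has 80% power at 0.83 SD. Against that, 0.05 / 0.83 = 6% and 0.20 / 0.83 = 24%.

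**5. What exit scores could recover.** Suppose half of the six leavers in the affected arm attend, and their exit scores stood in for the later outcome (a generous assumption). The observed arm mean then moves by (3 / 27) × δ. At δ = 0.5 that is 0.056 SD, leaving 0.100 − 0.056 = 0.044 SD uncorrected. The fix reduces the problem and makes it visible, but does not remove it.

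**The case against.** The strongest reply is that little is lost. A patient who leaves after treatment starts already has pain scores from each session attended, so only one further reading is missing. The drop in numbers is already budgeted by recruiting 30 to keep 24. Treatment effects on pain are secondary (section 3.4), while the primary outcome in section 3.3 concerns receptor binding against controls. Randomisation happens before Day 0, so some leavers may never have been stimulated. Only those willing to return would contribute.

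All of this stands, and it limits the point to a modest one. It does not explain why the questionnaires are omitted at a visit that takes place anyway.

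Four stronger readings are tempting, and the documents do not support them:
- That leavers give no pain outcome at all. Section 8.1.4 and Appendix A show otherwise.
- That Aim 2 will be analysed in completers only. The 24 evaluable per group may suggest it, but no section says so, and partial data could be used.
- That patients leave for lack of benefit or side effects. Section 11.2 gives neither reasons nor timing for the 20%.
- That capturing half the leavers would cut the standard error by about 6%, since √(24/27) = 0.943. This treats an exit score from any day as a scheduled follow-up value. A score taken during the first treatment week is not a Month 1 or Month 2 outcome and does not add to the number for those time points.

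**Conclusion.** The gap is real and appears in both the text and the schedule: the early-termination visit yields no pain score. It bears on up to 6 of 30 patients per arm under the plan's own allowance. The cost is possible bias in Aim 2, not power.

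The 0.05 to 0.20 SD rests on three assumptions: a completer contrast, 20% dropout, and a leaver-completer difference of 0.25 to 1.0 SD in one arm only. The error falls to zero when the difference and the dropout rate match across arms. Without scores at or after exit, the trial could not tell which case applies. This is a cheap improvement worth making before more patients leave, because the scores cannot be collected afterwards. It does not show that the planned comparison is invalid.

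**What to change.** 1. In section 7.6 and the Early Termination column of Appendix A, add the short McGill, VAS, GeoPain and a concomitant-medication review.
2. State in the analysis plan that these scores are analysed by randomised arm at their actual date, and are not used as Month 1 or Month 2 values.
3. In sections 5.6 and 7.6, separate stopping sessions from withdrawing consent. Ask patients who stop sessions but do not withdraw consent to complete the Week 1, Month 1 and Month 2 questionnaires. This does more for the comparison than an exit score, because the values fall at the planned times.
4. Leave H.O.P.E. out of the exit visit. Appendix A marks it only at the three follow-ups, so it has no baseline, and it is long, with space for up to 14 therapies.

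The cost is a few extra minutes per leaver with existing instruments. The limits are that exit scores come at varying times and that only leavers willing to return or respond contribute, so some bias remains.

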5.3. STRATEGIES FOR RECRUITMENT AND RETENTION

We will recruit 60 episodic migraine patients divided into 2 groups: 30 for the active M1 HD-tDCS group and 30 for the placebo HD-tDCS group. In addition, we will use the data from up to 10 healthy controls who were recruited and scanned during the NINDS-K23062946 project (IRBMED #HUM00027383; [name], Principal Investigator). We will then recruit healthy volunteers to a total of 30 age- and gender-matched healthy subjects.

Recruited patients will be screened from the UMClinicalStudies.org (formerly Engage) recruitment network and the University of Michigan. In addition to active referral from pain centers, advertisements will be placed in other pain clinics in the region. In-hospital advertisements will also be placed in pain clinics and departments at the institution, as well as across the university.

Subjects recruited will be prescreened by phone using an initial IRB-approved questionnaire. Those who pass the phone screening will be scheduled for an in-person Screening Visit, which will commence with a verbal and written informed consent process. Once informed consent has been obtained, subjects will undergo further screening by obtaining a history and performing a physical exam and QST. Those subjects who are determined to be eligible to enter the study will be enrolled into either the migraine or healthy volunteer pools; if migraine, they will be randomized to active or sham treatment.

Study duration per subject is expected to be less than 3 months; however due to the scheduling of PET and MRI visits, visit reminders (eg, phone and/or email; subject preference) may be implemented to help with retention.

During the course of participation, subjects will be compensated according to amounts stated in the informed consent form and approved by the IRB.

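### Section 7.6 gives reachable early leavers who decline a site visit no exit adverse-event contact and records them as lost to follow-up, including those terminated for an adverse event

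*Combined protocol and SAP*

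**What the plan says.** Section 7.6 sets its scope with "If a subject terminates the study early for one of the reasons listed in Section 5.5 or 5.6". Section 5.5 includes leaving at the subject's own wish ("Subjects are free to withdraw from participation in the study at any time upon request") and termination by an investigator when "Any clinical adverse event (AE), laboratory abnormality, or other medical condition or situation occurs" and staying in the study would not serve the subject. Section 5.6, on the handling of withdrawals, is one sentence: "Subjects wishing to withdraw from the study at any time may notify the study team".

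For early leavers willing to come back to the site, Section 7.6 lists two tasks: "Record adverse events as reported by subject or observed by investigator", and final instructions such as those on ongoing adverse events. For the rest, if the subject cannot be contacted, or "is not willing to return to the study site for a final study visit, the subject will be considered lost to follow up".

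In Appendix A the early-termination column carries only the adverse-event row. Its footnote 3 reads "If subject completes an in-person visit".

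Elsewhere the study already contacts subjects remotely. Prescreening is by phone (Sections 5.3 and 7.1), migraine patients are called on the morning of each scan (Section 8.1.3), and "visit reminders (eg, phone and/or email; subject preference) may be implemented to help with retention" (Section 5.3).

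**The concern.** The rule gives one status to two different people: someone the team cannot find, and someone who answers the phone but will not travel. Only the first is lost to follow-up in the usual sense. Because Section 7.6 takes in all of Section 5.5, the second group can include a subject whom the investigator removed for an adverse event.

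Two things are at stake. The first is exit safety information. Subjects who complete the study have adverse events collected up to the Month 2 visit (Day 65 ± 2) and are told what to do about ongoing events (Section 7.5). Early leavers get the equivalent only if they attend, although an unresolved event may be why they left.

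The second is the account of dropout. In a sham-controlled trial with 30 patients per arm, readers will want to know whether patients left the active and sham arms for different reasons. If the only status the protocol assigns is loss to follow-up, and no reason has to be recorded, that comparison may not be possible.

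**Working it through.** **Following the rule through.** Take a subject who leaves early, is reachable by phone and declines to travel.

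1. Scope: Section 7.6 applies whichever reason in 5.5 or 5.6 led to leaving. An adverse-event termination under 5.5 is not exempt.
2. Exit safety record: the adverse-event task and the final instructions are conditional on willingness to return to the site. This subject gets neither. Appendix A footnote 3 sets the same condition, so the schedule does not repair the text.
3. Status: the second limb of the closing sentence applies, so the subject is lost to follow-up, the same status as someone who could not be found.
4. Reason: Section 5.6 says only that the subject may tell the team. Sections 5.5, 5.6 and 7.6 do not require the reason, or who initiated the withdrawal, to be recorded.
5. Remote route: phone contact appears for prescreening, scan-day checks and optional reminders. E-mail appears only for the optional reminders. Neither is named as a route for exit safety contact.

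**How many subjects.** Inputs from Section 11.2: 24 evaluable per group and a possible 20% dropout. From Section 4: 30 active and 30 sham.

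- Plan's own figure: 24 / (1 − 0.20) = 24 / 0.8 = 30 per group. This reproduces.
- Early leavers at that allowance: 30 − 24 = 6 per arm, and 2 × 6 = 12 of 60 randomized patients.
- The share of these, f, who would be reachable but decline a visit is not given. It can lie anywhere from 0 to 1, so the number affected is 6 × f per arm: 0 at f = 0 and 6 at f = 1. Over both arms the range is 0 to 12 of 60.

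If an arm did have six leavers, one wrongly coded subject would be 1/6, about 17%, of that arm's dropouts. So a few cases could matter to a table of dropout reasons even though few patients are involved.

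**The case against.** The strongest reply is that the adverse events are not lost. Termination for an adverse event under Section 5.5 is an investigator's act, prompted by an event already identified. Appendix A collects adverse events at every visit from Screening on, and the tDCS side-effects form, which grades severity and relatedness, is scheduled from the stimulation sessions on. Investigator review (Section 15.1) and CRF documentation of expected, clinically significant events (Section 9.2.2) both apply before 7.6 does. Nothing in 7.6 says its label replaces the reason for termination. Subjects also hold physicians' contact numbers and a 24-hour emergency number, and are encouraged to report unusual symptoms (Section 2.3.1). All of this stands. A reader might infer that adverse-event discontinuations will be counted as unexplained loss and their safety data erased. The documents do not support that. What is missing is any required contact from the study's side after departure, and any required record of why the subject left.

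A second reply is that the Manual of Procedures, CRFs, Data Management Plan or separate SAP may hold disposition codes and contact rules. They may, and they are not available here. But the Supplemental Materials page says the supplemental documents it lists are not part of the protocol. A CRF that codes a declined visit separately would sit awkwardly with 7.6, so the text would still need reconciling.

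A reader might also blame this rule for missing pain data. That does not follow: subjects who do attend the early-termination visit complete no pain questionnaires either, so those gaps would exist whatever 7.6 said about non-attenders.

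Finally, the number affected could be zero. Section 11.1 reports that all 24 patients completed the group's previous HD-tDCS trial, although that trial had 5 daily sessions rather than 10 and a different pain condition. This is fair, and it is why no point estimate is given.

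**Conclusion.** The point holds as a defect in the disposition and exit-contact rule. Followed as written, Section 7.6 and footnote 3 give reachable subjects who decline a visit the wrong follow-up status, omit their exit adverse-event record and final instructions, and leave the reason for departure optional. A by-arm comparison of reasons for dropout may then not be possible. Information gathered before departure is unaffected.

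The size is 0 to 6 per arm, or 0 to 12 of 60. This assumes that dropout reaches but does not exceed the possible 20% used for sizing, and that any share of leavers could be reachable but unwilling. The documents support no narrower figure, and no adverse-event rate or difference between arms can be inferred from them. The change is worth making because exit information is hard to rebuild later and the cost is low. The point does not threaten the trial's main analyses.

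**What to change.** Amend Section 7.6 and Appendix A footnote 3 together:

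- If a subject declines the visit but accepts contact, collect adverse events and give the same final instructions by phone.
- Record the actual reason for leaving, and whether the subject or the investigator initiated it, in a field separate from follow-up status. Add this requirement to Section 5.6.
- Use lost to follow-up only for subjects who cannot be reached after a set number of attempts, stated in the protocol.
- Add a separate category for subjects who withdraw consent to further contact.

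These changes concern data collection and coding only; they alter no treatment or stopping rule. The cost is a short amendment, which needs IRB approval under Section 14.2, matching CRF fields if they do not already exist, and at most a few phone calls by staff who already call subjects.
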